9.6. Pharmacodynamics

9.6.1. *Dermal Blood Flow (DBF) Measurements by Laser Doppler Imaging (LDI) and Laser Speckle Contrast Imaging (LSCI)*

Dermal blood flow will be measured at visits and time points as specified in the Schedule of Activities (Section 2). All measurements for assessment should be performed while the participants are resting in a supine position on a comfortable bed in a quiet, ambient temperature-controlled room after at least 30 minutes acclimatization period.

Measurements of DBF will be taken with or without the application of a reactive agent to the skin. Based on the presumptive mechanism of action for LY3526318, CA will be used as the reactive agent to induce DBF.

Two methods will be used to measure DBF at each time point: DBF measurements from LDI (PeriScan PIM 3 system, Perimed, Stockholm, Sweden) and LSCI (PeriCam PSI System, Perimed, Stockholm, Sweden). The LDI assessment will be performed following LSCI assessment. The screening LDI measurements will be used to determine study eligibility.

Given that an upper extremity (forearm) requires approximately 5-days to recover from a reactive DBF measurement, the schedule between the screening and first study drug administration should account for this frequency limitation. During the first period, the extremity used for the first post-dose DBF measurements is chosen and the contralateral forearm

will be used for the 24-hour post-dose time point. Subsequent study periods should use the same schedule of DBF based on forearm and time point.

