6.1 Sample Size Considerations

The sample size is justified based on the statistical power to meet the primary endpoint of DBF measurements from LDI assay at t_{max} . The power calculation used 10% CA-induced absolute DBF in comparison between LY3526318 and placebo arms. For a 20% reduction in DBF (assuming mean observed placebo DBF of 444.3 arbitrary perfusion units (PU) with standard deviation (SD) of 55.1 PU) and a significance level of 0.05, a paired t-test with 16 patients results in 98% power to reject the null hypothesis. Incorporating a Bonferroni adjustment to account for multiplicity (changing the significance level to 0.05/3) lowers the power slightly to 96%.

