9.4.3 Hypothesis Testing

Significance testing will be 1-sided at the significance level of 0.05/3 for the primary statistical analysis.

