17.2 Pharmacodynamic Summaries

17.2.1 Descriptive Summary

The individual DBF measurements absolute values (all 5 time points) and percentage change from pre-CA (for post-CA at 3 and 24 hours post study drug) will be listed and summarized descriptively by treatment, timepoint, CA concentration and method.

The individual percentage change from pre-CA will be graphically presented with the treatments combined in a plot by subject, CA concentration and method. Additionally, combined individual plots will be presented, with all individual percentage change combined in a plot by treatment, CA concentration and method. The arithmetic mean (\pm SD) will be graphically presented with the treatments combined in a plot, by CA concentration and method.

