17.2.2 Statistical Analysis

An analysis of variance (ANOVA) will be performed on the percentage change (pre- to post-CA) at time points 3 h and 24 h post-dose using PROC MIXED in SAS. The percentage change will be used untransformed in the analysis. The model will include fixed effects for treatment, period, sequence, time and treatment*time interaction and a random effect for subject within sequence. The analysis will be done for each, method and CA concentration separately. From this model the least-squares means (LSMeans) for each treatment (including placebo) and the difference of the LSMeans for each of the active treatments with placebo at 3 h and at 24 h post-dose and the corresponding P value will be estimated for each method and CA concentration.

In the summary of the statistical analysis, it will be indicated that the result for LDI, 3 hours post-dose is the primary end point.

In SAS code:

```

proc mixed data=dbf;
  by CAconc method;
  class subject trtan time           period seq;
  model pchg = trtan time trtan*time period seq;
  random subject(seq);
  lsmeans trtan*time ;
  /*estimates*/
run;
quit;

```

For each of the active dose levels and CA concentrations, a decrease relative to placebo of the percentage change (pre- to post-CA) with a P value below (0.05/3) will be considered statistically significant.

Additionally, the same model (with fixed effects for treatment, period, sequence, time and treatment*time interaction and a random effect for subject within sequence) will be applied to the absolute values for each method and CA concentration separately, using data from all time points (i.e. pre study drug, 3 h pre- and post-CA, 24 h pre- and post-CA). From this model, using the absolute values, LSMeans and the differences with 90% CI and P-value will be estimated for each method and CA concentration for the following comparisons:

#	LSMean (absolute value) of	Compared with LSMean (absolute value) of
1	D1 post-CA at 3 h	Placebo post-CA at 3 h
2	D2 post-CA at 3 h	Placebo post-CA at 3 h
3	D3 post-CA at 3 h	Placebo post-CA at 3 h
4	D1 post-CA at 24 h	Placebo post-CA at 24 h
5	D2 post-CA at 24 h	Placebo post-CA at 24 h
6	D3 post-CA at 24 h	Placebo post-CA at 24 h
7	Placebo pre-CA at 3 h	Placebo pre study drug at 0 h
8	D1 pre-CA at 3 h	D1 pre study drug at 0 h
9	D2 pre-CA at 3 h	D2 pre study drug at 0 h
10	D3 pre-CA at 3 h	D3 pre study drug at 0 h
11	Placebo pre-CA at 24 h	Placebo pre study drug at 0 h

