12	D1 pre-CA at 24 h	D1 pre study drug at 0 h
13	D2 pre-CA at 24 h	D2 pre study drug at 0 h
14	D3 pre-CA at 24 h	D3 pre study drug at 0 h

In SAS code:

```

proc mixed data=dbf;
  by CACconc method;
  class subject trtan time           period seq;
  model aval = trtan time trtan*time period seq;
  random subject(seq);
  lsmeans trtan*time ;
  /*estimates*/
run;
quit;

```

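### The supplementary absolute-flow model gives resting and post-CA comparisons one common standard error, which is right for both only under equal variances and no participant-level interactions

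*SAP*

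**What the plan says.** SAP 17.2.2 first analyses percent change from pre- to post-CA, which is the primary analysis. It then states that the same model "will be applied to the absolute values for each method and CA concentration separately, using data from all time points". The five times per period are pre-drug, pre-CA at 3 h, post-CA at 3 h, pre-CA at 24 h and post-CA at 24 h. Fixed effects are treatment, time, their interaction, period and sequence. The only random statement begins "random subject(seq", that is, participant within sequence. There is no REPEATED statement and no grouping of the residual variance.

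From this fit, "LSMeans and the differences with 90% CI and P-value will be estimated for each method and CA concentration". The table lists 14 comparisons of two kinds:
- 1–6: post-CA flow, each active dose against placebo, at 3 h and at 24 h.
- 7–14: resting (pre-CA) flow at 3 h or 24 h against the same treatment's own pre-drug flow.

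Protocol 9.6.1 puts the two post-dose times on opposite arms: "the extremity used for the first post-dose DBF measurements is chosen and the contralateral forearm" serves the 24 h time point, and later periods repeat that arrangement. There is one pre-drug time point, and its forearm is not stated. On sizing, SAP 6.1 says "The power calculation used 10% CA-induced absolute DBF in comparison between LY3526318 and placebo arms".

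**The concern.** The model puts two physiological states into one error term. Entry requires at least a doubling of flow after CA (Protocol 6.1), so the states differ widely in mean. Equal spread is therefore doubtful, though not disproved. The model also assumes that a participant's two forearms, four periods and two states share one common shift. If any of this fails, the single SE is wrong for at least one group of comparisons.

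Comparisons 1–3 for LDI at 10% CA are the quantity the trial was sized on. Because the primary test uses percent change, this model is the only planned inferential analysis on that scale. Comparisons 7–14 show whether resting flow itself moves after dosing, which bears on reading a percent change from a resting value. At stake are the planned 90% CIs and P values, not the complete-data point estimates.

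**Working it through.** **Inputs.** 16 participants, four per sequence, four periods (SAP 6.2 and Table 1). Five readings per participant-period give 16 × 4 × 5 = 320 rows per method and CA concentration. Placebo post-CA mean 444.3 PU, SD 55.1 PU (SAP 6.1). The documents give no resting SD, participant share, correlation, forearm variance or period variance. Those are assumed below.

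**1. The plan's own figure.** The effect is 0.20 × 444.3 = 88.86 PU. With zero within-participant correlation the SD of a paired difference is 55.1 × √2 = 77.9 PU. A two-sided paired t-test with n = 16 has power 98.9% at 0.05 and 95.7% at 0.05/3, against the stated 98% and 96%. The documents state no SE for the absolute-flow model.

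**2. One SE for all 14.** The model has 20 treatment-by-time cells, 3 period terms and 15 participant terms (sequence included): rank 38, residual df 320 − 38 = 282. Each comparison is a difference of two means of 16 readings, so its model variance is MSE × 2/16 = MSE/8.

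**3. What the MSE estimates.** Let σ²R and σ²S be the resting and post-CA residual variances. Let σ²D be the variance of a participant's own stimulated-minus-resting shift, σ²F the participant-by-forearm variance per forearm, and σ²P the participant-by-period variance. Then

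E[MSE] = 0.600σ²R + 0.400σ²S + 0.255σ²D + 0.511σ²F + 0.745σ²P.

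- 0.600 and 0.400 are 3/5 and 2/5.
- 0.255 = 15 × (20 × 0.6 × 0.4)/282: 20 readings per participant split 12:8, with 15 directions left once time is fitted.
- 0.511 is twice that, because σ²F is per forearm and a difference between forearms has variance 2σ²F. It takes the pre-drug reading to be on one forearm.
- 0.745 = 42 × 5/282, with 64 − 16 − 3 − 3 = 42 participant-by-period directions.

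**4. True variances, times 8.**
- Comparisons 1–6: σ²S + σ²P.
- Comparisons 7–10: σ²R.
- Comparisons 11–14: σ²R + σ²F if the pre-drug reading is on the 3 h forearm. The two resting sets swap if it is on the other.

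Set all of these equal to E[MSE]. Equality of 7–10 and 11–14 gives σ²F = 0. Equality of 1–6 and 7–10 gives σ²R = σ²S + σ²P. Substituting, E[MSE] = σ²S + 1.345σ²P + 0.255σ²D must equal σ²S + σ²P. So 0.345σ²P + 0.255σ²D = 0, both are zero, and σ²R = σ²S.

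**5. Size with no stable participant differences** (share 0, no forearm or period variation). The true SE for 1–6 is √(55.1²/8) = 19.5 PU. Coverage is 2Φ(1.65 × ratio) − 1.

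| Assumed resting SD (PU) | E[MSE] | Model SE (PU) | Model/true SE, 1–6 | 90% CI coverage, 1–6 | Model/true SE, 7–14 |
|---|---|---|---|---|---|
| 10 | 1274 | 12.6 | 0.65 | 71% | 3.6 |
| 20 | 1454 | 13.5 | 0.69 | 75% | 1.9 |
| 30 | 1754 | 14.8 | 0.76 | 79% | 1.4 |
| 41.3 | 2238 | 16.7 | 0.86 | 84% | 1.15 |
| 55.1 | 3036 | 19.5 | 1.00 | 90% | 1.00 |

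Over resting SD 10–41.3 the model half-width for 1–6 is 1.65 × 12.6 = 20.8 to 1.65 × 16.7 = 27.6 PU. A post-CA-only fit would give 1.68 × 19.5 = 32.8 PU. Relative to 444.3 PU these are 4.7–6.2% against 7.4%.

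**6. Size with participant differences.** Use the same between-participant share of variance in both states. At share 0.75, correlation 0 and resting SD 10, E[MSE] = 0.6 × 25 + 0.4 × 759 + 0.255 × (75 + 2277) ≈ 918. The ratio is √(918/759) = 1.10 for 1–6 and √(918/25) = 6.1 for 7–14. At resting SD 41.3 the ratios are 1.39 and 1.9. The ratio for 1–6 crosses 1 at shares 0.69, 0.64, 0.56 and 0.40 (correlation 0) or 0.77, 0.83, 0.89 and 0.94 (correlation 1), for resting SD 10, 20, 30 and 41.3.

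**7. Period variation alone.** With equal totals and 30% participant-by-period, E[MSE] = 0.7 + 0.745 × 0.3 = 0.92. The ratio is √0.92 = 0.96 for 1–6 (88.7% coverage) and √(0.92/0.7) = 1.15 for 7–14 (94.2%).

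**8. Forearm variation.** Take resting SD 41.3, share 0.75, correlation 1, an added forearm SD of 25 PU and the pre-drug reading on the 3 h forearm. E[MSE] = 256 + 304 + 36 + 319 = 915. The ratio for 11–14 is √(915/(426 + 625)) = 0.93 (87.6% coverage), and for 7–10 it is √(915/426) = 1.47. The added component raises the total SDs to √(41.3² + 25²) = 48.3 and √(55.1² + 25²) = 60.5 PU.

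Simulation of 20,000 trials per scenario agrees within one percentage point: 71.0%, 74.0% and 84.2% for 1–6 at resting SD 10, 20 and 41.3, and 87.5% for 11–14 in step 8.

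**The case against.** The strongest reply is that nothing is decided on this model. It is an added analysis, and SAP 9.4.3 confines the formal rule: "Significance testing will be 1-sided at the significance level of 0.05/3 for the primary statistical analysis". At the planned 88.9 PU drop, neither SE changes the reading. This stands, and it limits the weight of the point.

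Second, harm is not shown from the documents. No resting SD or variance component is given, and share 0 is an extreme, although the stated power is consistent with it. In a middle range (share 0.5–0.6, correlation 0.5–0.8) the ratio for 1–6 is 0.91–1.02 at resting SD 41.3 and 0.83–0.93 at 30. This also stands: the structural fault is certain, but its size here is not.

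Third, comparisons 7–14 are not against placebo and mostly err towards wide intervals. That costs sensitivity rather than creating false findings. The forearm problem arises only if the pre-drug reading is on one arm. If so, four of the eight resting comparisons cross forearms and can be too narrow.

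Fourth, SAP 17.2.1 summarises absolute values by treatment and time point, so unequal spread would be visible, and SAP 3.0 allows changes reported in the CSR. But the descriptive SDs correct no interval or P value, and a change made after seeing them would be data-driven.

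The common SE is exact only with complete data. With one period missing for each of two participants, the SEs still run only from 0.354 to 0.365 times the residual SD.

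**Conclusion.** The concern holds. Following the SAP as written, the 14 comparisons share an SE that is right for both groups only under conditions the documents do not support. That result needs no assumed SD beyond the layout in SAP Table 1.

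The size does depend on assumptions. Across those tried, the model SE for comparisons 1–6 runs from 0.65 to 1.39 times the true value, so its direction is not determined. For 7–14 it is 1.4–6.1 times too large at resting SD 10–30 PU and 1.15–1.9 times at 41.3 PU, absent forearm variation. With forearm variation, four of those rows can be too narrow. A post-CA drop lying between the two half-widths, for example between 20.8 and 32.8 PU at resting SD 10 and share 0, would wrongly appear to exclude zero.

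The primary test is not affected by this mixing of states, and complete-data point estimates are unchanged. It should be corrected, but it does not threaten the primary conclusion.

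**What to change.** Split the absolute-flow analysis by state.

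- **Comparisons 1–6:** fit post-CA readings only, in separate models at 3 h and 24 h, with treatment, period and sequence fixed and participant random.
- **Comparisons 7–14:** use resting readings only, with participant-by-period and participant-by-time (forearm) effects. More simply, analyse the within-period difference (pre-CA minus pre-drug) separately at 3 h and 24 h, with treatment fixed, participant random and Satterthwaite df.

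A joint model with unstructured covariance across the five readings is possible. It would need participant-level variances that also differ by reading, up to 15 + 15 covariance parameters from 16 participants, so the separate fits are simpler.

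In eight simulated scenarios, including forearm and period variation, the separate fits gave 89.7–90.2% coverage for comparisons 1–3 and for 7–14 in the difference form.

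The cost is a few lines of SAS and one paragraph of SAP text, with no new data. For 1–6 the df fall from 282 to 64 − 22 = 42, and the 90% CI multiplier rises from 1.65 to 1.68. For 7–14 the df fall to 90 in the resting-only fit, or to about 30–60 in the difference form (multiplier 1.67–1.70).

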During each visit (screening and study periods), each patient will undergo at least 30 minutes acclimatization and placement of 3 rubber O-rings on the volar surface of the forearm. Prior to study drug administration, a pre-drug DBF will be collected without CA. For each time point following study drug administration, pre-CA measurements will be performed for the areas defined by the rings within 10 minutes before CA application. After the pre-CA measurements, a 20 μ L topical dose of 10% CA will be applied in the proximal O-ring of the participant's forearm. Using the same procedure, a 20 μ L topical dose of 3% CA will be applied in the medial ring, followed by a 20 μ L topical dose of the vehicle solution to the distal ring. LDI/LSCI measurements will again be performed approximately 20 minutes after CA and vehicle applications. Specific details of the procedure will be agreed upon and documented between the sponsor and investigator and research staff operating the equipment.

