6.0 Study Design

This is a Phase 1 randomized, double-blind, placebo-controlled, 4-way crossover study of LY3526318 in healthy female participants.

All participants will have 2 screening visits with the first to evaluate the health of the participant and the second visit to undergo an LDI assessment to ensure a response of at least 100% increase in DBF between pre- and post-CA challenge. Following a screening period of up to 28 days, eligible participants will be confined to the clinical research unit from Day 1 until all assessments are completed on Day 2 of each dosing period.

As summarized in [Table 1](#), each participant will be randomly assigned to 1 of 4 treatment sequences, with a ratio of 3 LY3526318: 1 placebo. Each participant will receive 3 doses of LY3526318 and 1 dose of placebo in a crossover manner, with at least 6 days of washout between doses. The planned dose levels of LY3526318 are anticipated not to exceed the maximum administered dose in the SAD portion of Study CVAA.

Table 1 Treatment Sequence

Sequence	N	Period 1	Period 2	Period 3	Period 4
P132	4	P	D1	D3	D2
12P3	4	D1	D2	P	D3
231P	4	D2	D3	D1	P
3P21	4	D3	P	D2	D1

During each visit (screening and study periods), each patient will undergo at least 30 minutes acclimatization and placement of 3 rubber O-rings on the volar surface of the forearm. Prior to study drug administration, a pre-drug DBF will be collected without CA. For each time point following study drug administration, pre-CA measurements will be performed for the areas defined by the rings within 10 minutes before CA application. After the pre-CA measurements, a 20 μ L topical dose of 10% CA will be applied in the proximal O-ring of the participant's forearm. Using the same procedure, a 20 μ L topical dose of 3% CA will be applied in the medial ring, followed by a 20 μ L topical dose of the vehicle solution to the distal ring. LDI/LSCI measurements will again be performed approximately 20 minutes after CA and vehicle applications. Specific details of the procedure will be agreed upon and documented between the sponsor and investigator and research staff operating the equipment.

All assessments will be performed as defined in Schedule of Activities ([Appendix 2: Schedule of Assessments](#)).

All participants will attend a safety follow-up visit about 7 days following the last dose of study drug.

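### Resting-flow comparisons 7–14 are fitted by CA concentration alongside post-CA readings, so each is reported two or three times per method, with an interval that depends on post-CA variability

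*SAP*

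**What the plan says.** SAP 17.2.2 describes a second model, "applied to the absolute values for each method and CA concentration separately, using data from all time points". The time points are pre-drug, 3 h pre- and post-CA, and 24 h pre- and post-CA. The code runs it "by CACconc method", with a random subject effect. It has no ring term and no statement that lets the residual variance differ between resting and post-CA readings.

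All 14 comparisons come from each fit: "LSMeans and the differences with 90% CI and P-value will be estimated for each method and CA concentration for the following comparisons". Rows 1–6 compare active with placebo after CA. Rows 7–14, from "Placebo pre-CA at 3 h" to "D3 pre-CA at 24 h", compare a pre-CA reading with the pre-drug reading of the same treatment.

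On the readings themselves, SAP 6.0 describes "placement of 3 rubber O-rings on the volar surface of the forearm" and says: "Prior to study drug administration, a pre-drug DBF will be collected without CA". Protocol 9.6.1 says that after dosing "pre-CA measurements will be performed for the areas defined by the rings within 10 minutes before CA application". The 10% solution then goes in the proximal ring, 3% in the medial ring and vehicle in the distal ring.

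**The concern.** None of the readings in rows 7–14 has CA on the skin in that session. CA concentration is a real factor in rows 1–6. In rows 7–14 it only identifies the ring.

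Two things follow. First, one resting contrast is reported several times per method, each time from one ring, and the SAP has no rule for which result counts if they differ. Second, the residual variance behind each interval is pooled over resting and stimulated readings. If post-CA flow varies more than resting flow, the resting contrasts inherit that extra spread, and most of all in the ring with the strongest stimulus. The same resting question would then carry different interval widths for reasons unrelated to resting flow.

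What is at stake is a supportive check. Pre-CA flow is the denominator of the percentage change, so readers will look at rows 7–14 when they interpret that result.

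**Working it through.** **The plan's own figure.** SAP 6.1 gives a placebo mean of 444.3 PU, SD 55.1 PU, a 20% reduction, n = 16, and power of 98% at 0.05 and 96% at 0.05/3. The difference is 0.20 × 444.3 = 88.86 PU. With an SD of the paired difference of 55.1 × √2 = 77.9 PU, the two-sided paired t-test (15 df) has power 98.9% and 95.7%. This is close to the stated figures, and it implies that 55.1 was used as the error SD of a single post-CA reading with no within-participant correlation. The point does not rest on the power figure.

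**Count.** Rows 7–14 are 8 contrasts, and there are 2 methods: 8 × 2 = 16 distinct contrasts. By CA concentration they become 8 × 2 × 2 = 32, or 8 × 2 × 3 = 48 if vehicle is a level. The SAP does not say which.

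**Effect of the shared residual variance.** Inputs: 16 participants; 5 readings per period and ring, of which 3 are resting and 2 post-CA; post-CA SD 55.1 PU for 10% CA (SAP 6.1). Assumed: resting SD 12 PU, post-CA SD 35 PU for 3% CA and 12 PU for vehicle, and independent errors between readings.

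- Pooled residual variance = (3 × resting SD² + 2 × post-CA SD²) / 5.
- SE of a within-treatment contrast = √(pooled variance × 2/16). The true SE is resting SD × √(2/16) = 12 × 0.3536 = 4.24 PU.

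| Stratum | Pooled variance | Model SE (PU) | True SE (PU) |
|---|---|---|---|
| 10% | (432 + 6072.0)/5 = 1300.8 | 12.75 | 4.24 |
| 3% | (432 + 2450)/5 = 576.4 | 8.49 | 4.24 |
| Vehicle | (432 + 288)/5 = 144 | 4.24 | 4.24 |

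A simulation of the SAP layout (320 readings per ring, 282 residual df) agrees: mean model SEs of about 12.75, 8.5 and 4.24 PU, and an empirical SD of the contrast of 4.1 to 4.4 PU in every stratum.

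Range for the 10% stratum:

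- Resting SD 6 PU: (108 + 6072.0)/5 = 1236.0, model SE 12.43 against 2.12 PU.
- Resting SD 24 PU: (1728 + 6072.0)/5 = 1560.0, model SE 13.96 against 8.49 PU.
- Resting SD 12 PU, with the subject effect absorbing half of the post-CA variance (3036.0/2 = 1518.0): (432 + 3036.0)/5 = 693.6, model SE 9.31 against 4.24 PU.

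**Effect of averaging rings.** With correlation ρ between rings, the SE of a k-ring mean relative to one ring is √((1 + (k − 1)ρ)/k). For k = 3:

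| ρ | SE ratio | Single-ring interval wider by |
|---|---|---|
| 0 | 0.58 | 73% |
| 0.5 | 0.82 | 22% |
| 0.75 | 0.91 | 10% |
| 0.9 | 0.97 | 3.5% |
| 1 | 1.00 | 0% |

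Under the assumed SDs, removing the post-CA readings takes the 10% stratum from 12.75 to 4.24 PU. Averaging three rings then gives 4.24 × 0.816 = 3.46 PU at ρ = 0.5, or 4.24 × 0.966 = 4.10 PU at ρ = 0.9. The first step does most of the work.

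**The case against.** The best defence is ring-matching. Percentage change is analysed by CA concentration, each concentration sits in a fixed ring, and so the denominator of the 10% result is resting flow in the proximal ring. A three-ring mean is the denominator of no endpoint. The documents also do not show that the three positions behave alike, and from period 2 their skin has had different earlier exposure. Protocol 9.6.1 puts recovery at about 5 days, and Section 5.1 requires at least 6 days of washout.

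This is a reason to keep ring-level resting values visible, and SAP 17.2.1 already lists and summarises them by CA concentration. It does not justify the planned contrasts: rows 7–14 feed no percentage-change analysis, the SAP gives no ring-matching reason, and matching does not explain why post-CA spread should set a resting interval.

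Other objections stand and limit the point:

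- A reader might infer that the other rings are discarded. They are not; each is analysed in its own BY group.
- A reader might take rows 7–14 as a test of whether the drug changes resting flow. They are changes from pre-drug within each treatment, placebo included. A drug effect would need active minus placebo, which neither these rows nor the fix supplies.
- A reader might count expected false positives at 0.05. The SAP sets no significance rule for these rows; the 0.05/3 rule belongs to the percentage-change analysis.
- The 24 h readings use the contralateral forearm, and the documents do not say which forearm gives the pre-drug reading. Ring averaging does not settle that for rows 11–14.

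**Conclusion.** The point holds as a minor one. From the text and code alone, each resting contrast is produced two or three times per method, from one ring each, in a model that shares one residual variance with post-CA readings.

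The size is conditional. The threefold SE in the 10% stratum (12.75/4.24 = 3.0) needs a resting SD well below the post-CA SD. The documents give only the latter, and using it as residual SD follows the plan's own power calculation. Across the cases shown, the ratio of model to true SE runs from 13.96/8.49 = 1.6 to 12.43/2.12 = 5.9. The further gain from ring averaging could be nil, because the between-ring correlation is not given.

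One ring per stratum is explicit for the pre-CA readings. For the pre-drug reading it is inferred from ring placement at each visit and from the summary of all five time points by CA concentration. If a single forearm value is recorded instead, it is repeated in every stratum.

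A reader might infer that the primary result is at risk. It is not: LDI percentage change at 3 h comes from a separate model that this issue does not touch.

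**What to change.** Take rows 7–14 out of the model run by CA concentration. For each method, fit one model to the unstimulated readings only (0 h, 3 h pre-CA, 24 h pre-CA), using the ring mean per participant, period and time, or ring as a repeated factor. Report rows 7–14 once per method. Keep rows 1–6 by CA concentration, and keep ring-level resting values in the listings and descriptive tables. State whether the 0 h reading is recorded per ring and on which forearm, and whether vehicle is a BY level.

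The cost is a wording change in SAP 17.2.2 and a small programming change, with no new data and fewer outputs. The one small loss is that ring-specific resting contrasts would be shown only descriptively.
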